## 6.4. Screening Phase

See [Section 10.1](#) and [Section 10.2](#).

## 6.5. Treatment Phase

All subjects enrolled in the trial will be treated for 24 weeks across six 28-day treatment cycles.

In total, 9 doses of MOR202 will be administered on the following treatment days: Cycle 1 Day 1, 8, 15 and 22, and on Day 1 of Cycle 2 to 6 (for details see [Figure 1](#) and [Table 2](#)).

The Treatment Phase ends with the EOT visit, scheduled between 28 and 42 days after the last administration of MOR202. For details see [Section 10.4](#).

## 6.6. Follow-up Phase

The follow-up phase consists of 28 weeks of post-treatment follow-up starting from the EOT visit. It consists of two visits at an interval of 14 weeks each.

The follow-up phase ends with the EOS visit, scheduled 28 weeks after the EOT visit. For details see [Section 10.5](#).

## 6.7. Clinical Trial Duration

The duration of this trial is planned to be approximately 2 years from first subject signing the informed consent form (ICF) until trial completion.

Subjects will be on the clinical trial from signing of ICF until the EOS visit (i.e. a planned maximum time period of 58 weeks: up to 6-week screening phase, 24-week treatment phase and 28-week follow-up phase).

## 6.8. Risks and Benefits to Subjects

CCI

Similar safety findings were also observed in the FiH trial MOR202C101 (see [Section 4.2](#) and [Section 6.1.2](#)). In this trial administering MOR202 to MM subjects the most frequent MOR202 related treatment emergent adverse events (TEAEs) were thrombocytopenia, neutropenia, lymphopenia, and infections. No ADAs were detected in this trial until the primary completion date (samples analyzed from 85 subjects treated for up to 29 months at a maximum) ([Jarutat 2018](#)).

It is expected that the potential risks as described above will be adequately controlled by the design of this trial (e.g. by the inclusion and exclusion criteria) as well as by frequent monitoring for potential ADRs. Since a major pharmacological effect of MOR202 is depletion of plasma cells and plasmablasts, the risk for a potentially reduced function of the adaptive immune system was further addressed. This comprises monitoring and potential substitution of total serum immunoglobulin as well as vaccination before trial start (see Section 7.1 and Section 7.2).

MOR202 offers a novel mechanism of action that may have the potential to emerge as an important treatment option for aMN patients compared to current (off-label) treatment options. Particularly with calcineurin inhibitors (CNIs) being intrinsically nephrotoxic and cyclophosphamide as an alkylating cytotoxic drug being associated with known hematotoxicity, risk of ovarian insufficiency and secondary malignancy, new therapeutic options are needed for the treatment of MN. Recent literature suggests that RTX, although more favorable in the safety profile compared to the aforementioned drugs, might have decreased activity in high antiPLA2R antibody titer subjects (Ruggenti et al 2015). This patient population is specifically addressed by Cohort 1 of this trial.

Non response to an immunosuppressive regimen may be caused by survival of long-lived plasma cells producing anti-PLA2R antibodies. These cells demonstrate a high expression of MOR202's target CD38. This patient population is specifically addressed by Cohort 2 of this trial.

In this context and taking into account the existing clinical experience with MOR202, the overall risk/benefit ratio for the trial subjects is regarded as acceptable.

## 7. SELECTION OF SUBJECTS

All subjects must sign the ICF and must meet the following selection criteria at screening to participate in the trial.

### 7.1. Inclusion Criteria

Since deviations from inclusion criteria can have a negative impact on subject safety or the scientific integrity and regulatory acceptability of the clinical trial, the Sponsor will not provide waivers to them (*parameters in italics will be tested at screening; parameters not in italics will be determined locally*):

Cohort 1 and 2:

1.  $\geq 18$  to  $\leq 80$  years (at date of signing ICF).
2. *Urine protein to creatinine ratio (UPCR) of  $\geq 3.000$  g/g OR proteinuria  $\geq 3.500$  g/24 h from 24 h urine at screening.*
3. **Anti-PLA2R antibody positive MN in need of IST according to the investigator's judgment. The diagnosis of MN should be histologically documented with a diagnostic biopsy; for this purpose, a biopsy at screening or an archival biopsy acquired within 5 years prior to screening is acceptable.**
4. *Estimated glomerular filtration rate (eGFR)  $\geq 50$  mL/min/1.73 m^2. Alternatively eGFR  $\geq 30$  and  $< 50$  mL/min/1.73m^2 and interstitial fibrosis and tubular atrophy (IFTA) score  $< 25\%$  in a renal biopsy obtained within the last 6 months prior to start of screening (if not available, a biopsy should be performed at screening to obtain the IFTA assessment).*

5. Not in spontaneous remission despite proper treatment with ACEIs, ARBs (sufficient dose and treatment duration) as per clinical practice and scientific guidelines. If the Principal Investigator determines that a subject is intolerant to an ACEI or ARB, the reason must be documented and approval obtained from the Medical Monitor prior to enrolment.
6. Systolic blood pressure (BP)  $\leq$  150 mmHg and diastolic BP  $\leq$  100 mmHg after 5 minutes of rest.
7. Subject vaccinated against Pneumococcus within the last 5 years prior to date of signing ICF (subjects may be vaccinated to meet this criterion during screening; interval to first dose of MOR202 must be at least 14 days [MSD SmPC]).
8. Cohort 1 comprises newly diagnosed or relapsed subjects: *Serum anti-PLA2R antibodies  $\geq$  50.0 RU/mL determined at screening by Euroimmun ELISA at central laboratory.*
9. Cohort 2 comprises therapy refractory subjects:
  - a. Subject did not achieve immunological remission after prior IST(s) as documented by the investigator AND
  - b. Subject is without promising standard therapeutic options as documented by the investigator (i.e. investigator expects efficacy or safety issues with remaining IST options) AND
  - c. *Serum anti-PLA2R antibodies  $\geq$  20.0 RU/mL measured at screening by the Euroimmun ELISA at central laboratory.*

CCI

Note: France will only enroll patients in Cohort 2.

## 7.2. Exclusion Criteria

Since deviations from exclusion criteria can have a negative impact on subject safety or the scientific integrity and regulatory acceptability of the clinical trial, the sponsor will not provide waivers to them. Subjects must be excluded from participating in this clinical trial if they meet any of the following criteria at screening (*parameters in italics will be tested at screening; parameters not in italics will be determined locally*):

1. *Hemoglobin*  $\leq 80$  g/L‡
2. *Thrombocytopenia: Platelets*  $\leq 100.0 \times 10^9/L^*$
3. *Neutropenia: Neutrophils*  $\leq 1.5 \times 10^9/L^\#$
4. *Leukopenia: Leukocytes*  $\leq 3.0 \times 10^9/L^\#$
5. *Hypogammaglobulinemia defined as serum immunoglobulin*  $\leq 4.0$  g/L‡
  - f Subjects may receive blood transfusions or erythropoietin to meet the criterion.
  - \* Subjects may receive thrombopoietin to meet the criterion.
  - # Subjects may receive colony stimulating factors to meet the criterion.
  - ‡ Subjects may receive immunoglobulin substitution to meet the criterion.
6. *B-cells*  $\leq 5 \times 10^8/L$ .
7. Secondary cause of MN (e.g. SLE, medications, malignancies) as determined by the investigator.
8. Concomitant renal disease other than MN (e.g., diabetic renal disease, lupus nephritis, IgA nephropathy).

CCI

CCI

## **8. TREATMENT OF SUBJECTS**

### **8.1. Prior Therapy**

The following prior therapy will be recorded in the eCRF:

- All prior medications/non-drug procedures given for MN.
- All prior immunosuppressive medications.
- All other medication and other therapy (including non-drug procedure) taken by/administered to the subject within 30 days prior to signature of ICF.

The entry must include the dose, regimen, route of administration, indication, and dates of use (start, end).

### **8.2. Investigational Medicinal Product (IMP)**

Each Investigator is responsible for ensuring that deliveries of IMP(s) and other clinical trial materials from the sponsor are completely and correctly received, recorded, handled and stored safely and properly in accordance with all applicable regulatory guidelines, and used in accordance with this clinical trial protocol.

The IMP must be stored in a secure area under the appropriate physical conditions for the product. Access to and administration of the IMP will be limited to the Investigator or designee. The IMP must be dispensed or administered only to subjects enrolled in the clinical trial and in accordance with the protocol. After the clinical trial and overall drug accountability, all unused IMP must be returned to the sponsor or destroyed on site following the Drug Handling Manual.

#### **8.2.1. MOR202**

MOR202 antibody (i.e. compound MOR03087, this protocol refers to as MOR202) will be supplied by the sponsor as a lyophilized powder for reconstitution in labelled glass vials. MOR202 must be stored at 2-8°C until use.

MOR202 will be labelled according to applicable regulatory requirements. All chemical, physical and pharmaceutical characteristics are summarized in the Investigator's Brochure.

#### **8.2.2. Preparation and application of MOR202 including prophylaxis of infusion reactions**

MOR202 will be administered i.v. at a dose of 16 mg/kg. Preferably, body weight data will be collected in the morning of the dosing day. In case this is not possible, the MOR202 dose must be based on a weight determined within 14 days prior to dosing.

For administration, CCI

The individual MOR202 infusion will be prepared under aseptic conditions and administered at the trial site according to the directions of the Drug Handling Manual.

CCI

### 8.3. Concomitant Therapy

Subjects are allowed to continue medications that they are taking at baseline, particularly, supportive therapy for MN and therapy initiated at screening such as immunoglobulin substitution or erythropoiesis stimulating agent (ESA) therapy. Subjects are allowed to receive concomitant medications that are medically indicated as standard of care for the treatment of symptoms and intercurrent illnesses, unless they fall under prohibited medications. Subjects may also receive therapy to mitigate side effects of the trial medication as clinically indicated, as well as best supportive care as per institutional guidelines. This may include medications such as diuretics, anti-lipid-medication, anti-hypertensive (e.g. ACEI), anticoagulation, antiemetics, antidiarrheals, anticholinergics, antispasmodics, antipyretics, antihistamines, analgesics, or antibiotics. The Investigator should instruct the subject not to take any additional medications (including over-the-counter products) during the trial without prior consultation.

Investigators should document all medication and other therapy (including non-drug procedure) taken by/administered to the subject during the entire course of the trial including the screening and the follow-up phase. The entry must include the dose, regimen, route of administration, indication, and dates of use (start, end).

#### 8.3.1 Management of Infusion Related Reactions (IRRs)

If a subject presents with a grade 1 or 2 infusion reaction:

- The infusion should be stopped immediately.
- The subject should receive appropriate further treatment with an antihistamine, paracetamol (acetaminophen), and glucocorticoids as clinically indicated.

- Once the symptoms have been resolved or reduced to “mild” according to the investigator’s assessment, the infusion can be continued at an infusion rate of 50% of the initial rate. If, after 1 hour, the subject is symptom-free and vital signs are stable, the infusion rate may be increased every 30 minutes by approximately 25% of the reduced rate as tolerated.
- If a subject who developed a grade 1 or 2 IRR will receive further infusions, then premedication with glucocorticoids either as mandated by this protocol or by local guidelines should be given before start of any subsequent MOR202 infusion. The infusion rate should be slowed down and the duration of infusion should exceed that of the last prior infusion by at least 30 minutes.

**If a subject exhibits a grade 3 IRR:**

- The infusion should be stopped immediately.
- The subject must receive appropriate treatment with an antihistamine, paracetamol (acetaminophen), and glucocorticoids and, as necessary, further medications (i.e. epinephrine, bronchodilator).
- Only after the resolution of all symptoms to  $\leq$  grade 1, and after having received appropriate prophylactic medication(s) as described above, the infusion may be resumed at an infusion rate of 25% of the initial rate. If, after 1 hour, the subject’s symptoms do not return and vital signs are stable, the infusion rate may be increased to a maximum of 50% of the initial rate.
- If, after the resumption of the infusion, symptoms return (irrespective of grade), the infusion must be discontinued for that visit date and the infusion tubing should be disconnected. Based on the investigator’s decision, the subject may receive further MOR202 at the next scheduled visit provided clinically appropriate precautions were taken.
- If a subject who developed a grade 3 IRR will receive further infusions, then premedication with glucocorticoids either as mandated by this protocol or by local guidelines should be given before start of any subsequent MOR202 infusion. The infusion rate should be slowed down and the duration of infusion should exceed that of the last prior infusion by at least 30 minutes.

**If a subject presents with a grade 4 IRR:**

- The infusion must be discontinued immediately and the infusion tubing should be disconnected.
- The subject must receive appropriate treatment with an antihistamine, paracetamol (acetaminophen), and glucocorticoids and, if necessary, further medications (i.e. epinephrine, bronchodilator).
- The subject must not receive any further MOR202 infusion and must discontinue trial treatment, subject may enter the follow-up phase.

### 8.3.2 Infection Prophylaxis

The immunoglobulin level will be monitored throughout the trial. If this level drops below 4 g/L, initiating substitution therapy with a polyvalent immunoglobulin according to local institutional guidelines is advised. Generally, a trough level of at least 5 g/L shall be targeted, with a substitution of 0.2 g per kg body weight every 3 to 4 weeks.

Furthermore, investigators may follow institutional guidelines on infection prophylaxis for subjects regarded to be at high risk of infection.

### 8.4. Prohibited Therapy: Immunosuppressive therapies (IST)

The use of ISTs other than MOR202 is prohibited during the entire trial. This includes, but is not limited to ACTH, chemotherapies, immunotherapy, biological response modifiers, mAbs with or without conjugation, CNIs (e.g. cyclosporine, tacrolimus), plasmapheresis and immuno-adsorption. MOR202 treatment of subjects in need of immunosuppressive therapies must be discontinued and the subject must be discontinued from the trial (see Section 8.8.5).

Subjects in need of systemic corticosteroid therapy other than for prophylaxis and treatment of IRR for more than 7 days may continue being treated with MOR202, but will be excluded from the Per Protocol Analysis Set and the Immunological Analysis Set (IAS).

### 8.5. Treatment Adherence

Subjects will receive MOR202 under the direct supervision of site personnel. Each administration volume or dose will be checked.

The vial/outer package code and volume or dose per administration will be recorded in each subject's eCRF as well as in the source data. At each visit after initiation of treatment, site staff will record adherence of subjects to their assigned regimen.

Non-adherence is defined as administering  $\leq 70\%$  or  $>$  CCI of a MOR202 dose.

Any MOR202 dose missed without a medical reason is considered a non-adherence.

### 8.6. Overdose

In this clinical trial, an overdose of MOR202 is defined as a dose exceeding CCI of the planned dose.

In clinical trial MOR202C101, four incidents of doses exceeding the calculated dose were noted, all of these doses exceeded the planned dose by no more than 10.5% and affected subjects remained asymptomatic.

In case of overdose, infusion should be discontinued immediately and subjects should be closely monitored for signs or symptoms of AEs for 24 hours, and appropriate symptomatic treatment instituted immediately if needed. No specific antidote is available. Overdose with clinical symptoms will be reported as AE (non-serious or serious) in accordance to Section 10.8.10.

### 8.7. Treatment management of subjects with toxicity

For the first dosing of MOR202, subjects should exhibit hemoglobin, leucocyte, neutrophil and platelet counts meeting the eligibility criteria. They should not have an active infection  $\geq$  grade 2.

For subsequent doses, in case a subject shows laboratory values as listed below, further treatment of the subject has to be interrupted:

- Hemoglobin level < 60 g/L (grade 3): interruption until resolved to  $\geq 80$  g/L.
- Platelet count <  $75.0 \times 10^9/L$  (grade 2): interruption until resolved to  $\geq 100.0 \times 10^9/L$ .
- Neutrophil count <  $1.000 \times 10^9/L$  (grade 3): interruption until resolved to  $\geq 1.500 \times 10^9/L$ .

If the subject exhibits any other clinically relevant adverse drug reaction  $\geq$  grade 3, MOR202 administration has to be interrupted until the toxicity has resolved to grade 2 or better.

## **8.8. Subject Discontinuation of IMP and Subject Withdrawal**

### **8.8.1. Discontinuation due to toxicity**

MOR202 treatment must be permanently discontinued, if:

- Needing platelet transfusion.
- Not recovering to  $\leq$  grade 2 from  $\geq$  grade 3 ADRs related to MOR202 within 21 days despite adequate treatment of the ADR.
- Experiencing grade 4 IRR.

Subjects discontinuing MOR202 treatment will have their EOT visit (earliest after 28 days after last dose of MOR202) and enter the follow-up phase.

### **8.8.2. Discontinuation due to other reasons**

MOR202 treatment must be permanently discontinued for subjects:

- With progressive disease as defined in [Section 3.2](#)
- Wishing to discontinue MOR202 treatment
- With pregnancy

Investigator(s) have the right to discontinue subjects from MOR202 treatment in the event of illness, AEs, or other reasons putting a risk to the health or well-being of the subject, or in case of lack of subject's co-operation.

The reason for discontinuing MOR202 treatment must be noted in the eCRF.

Subjects discontinuing MOR202 treatment will have their EOT visit (earliest after 28 days after last dose of MOR202) and enter the follow-up phase.

### **8.8.3. Discontinuation due to efficacy - stringent immunological complete remission**

Furthermore, treatment may be discontinued for subjects with stringent immunological complete remission (sICR) confirmed by repeat measurement at least 25 days apart. These subjects will follow their planned schedule, but will not be treated at the following CxDI visits, unless a subject turns positive again during the treatment phase.

### **8.8.4. Withdrawal due to Subject Decision**

Each subject is free to withdraw from the clinical trial at any time. All efforts will be made to complete and report the observations up to the time of withdrawal as thoroughly as possible. A complete final evaluation at the time of the subject's withdrawal should be made (all assessments scheduled for EOT/EOS visit depending on time of withdrawal). An explanation why the subject

is withdrawing from the clinical trial should be provided. If withdrawn in the treatment phase, these subjects will not enter the follow-up phase.

#### **8.8.5. Withdrawal due to Use of Prohibited Therapy [Immunosuppressive Therapy]**

Subjects starting on prohibited IST other than MOR202 will be withdrawn from the clinical trial. If withdrawn in the treatment phase, these subjects will immediately be scheduled for their EOT visit (at least 28 days after the last MOR202 dose) and will not enter the follow-up phase.

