## 5. ~~CLINICAL TRIAL PURPOSE AND OBJECTIVES~~

The purpose of the trial is to assess the safety and efficacy of the human anti-CD38 antibody MOR202 in subjects with aMN in two cohorts with subjects:

- Presenting with medium/high anti-PLA2R titer either newly diagnosed or after relapse and eligible for IST (Cohort 1) or
- With aMN refractory to IST (Cohort 2).

	Objective	Endpoint
Primary	To assess the safety and tolerability of MOR202 treatment in subjects with aMN.	Incidence and severity of TEAEs.
Key Secondary	To assess the effect of MOR202 on serum antiPLA2R antibodies in subjects with aMN.	Best immunological response: rate of sICR, ICR and IPR based on reduction of serum anti-PLA2R antibody titer.
Secondary	To assess the immunogenicity of MOR202 (anti-MOR202 antibody formation) in subjects with aMN.	Number and antibody titers of subjects tested positive for anti-MOR202 antibodies.
	To assess the PK profile of MOR202 in subjects with aMN.	MOR202 serum concentrations after multiple i.v. administrations.
	To assess the safety in subjects with aMN after MOR202 treatment and during the follow-up phase.	Incidence and severity of AEs in the follow-up phase.
Exploratory	CCI	

	
CCI
 
	
Additional exploratory analyses may be performed to characterize further potential pharmacodynamic biomarkers under MOR202 treatment.
 
CCI
 

• Changes in peripheral blood immune cell populations.

 
CCI
 

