All serious and non-serious AEs must be followed up for a final outcome until the end of the follow-up phase. Subjects prematurely withdrawn from the clinical trial will be followed up at least until 28 days after last IMP treatment. A final outcome of "unknown" is not considered acceptable. A final outcome of "not yet resolved" is acceptable.

The subjects will be closely observed and questioned for any kind of AE during the clinical trial procedures and at follow-up appointments throughout the clinical trial period with non-leading questioning (e.g. "How do you feel?"). The subjects will be instructed to immediately report any symptoms and signs to the site personnel (i.e. between formal observations).

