### Proteinuria Response

Proteinuria responses are reflected by the reduction of proteinuria as measured by UPCR. Based on the proteinuria responses, the following response categories are defined by this clinical trial:

- Proteinuria Complete Response (Prot-CR): Reduction of proteinuria to less than 0.5 g/g, serum albumin within the reference range (3.5 – 5.2 g/dL) and stable eGFR (at least 80% of baseline)
- Proteinuria Partial Response (Prot-PR): Reduction by at least 50% of UPCR at a given visit compared to baseline, proteinuria below 3.0 g/g and stable eGFR (at least 80% of baseline), but not meeting Prot-CR

The following variables related to proteinuria responses are defined as follows.

Overall Proteinuria Response (OPR), defined as subjects achieving either Prot-CR or Prot-PR as a response (irrespective of start of prohibited medication or progressive disease prior to the proteinuria response).

Time to First Proteinuria Response (in months) prior to start of prohibited treatment or progression, defined as

[Date of first documented response of Prot-CR or Prot-PR (whichever is earlier) – Start of study drug + 1 day]/30.4375

Best Proteinuria Response (BPR) for a subject is defined when a subject is classified as having a Prot-CR or Prot-PR at any time during the trial but prior to start of prohibited treatment or progression. Responses for BPR are ordered as Prot-PR < Prot-CR. If a subject meets the criteria for more than one response category, the subject will be classified in the highest category.

Time to BPR (in months), defined as

[Date of BPR – Start date of study drug + 1 day]/30.4375

Duration of Proteinuria Response, defined as

[Date of death, PD or start of prohibited treatment (whichever is earlier) – Date of first documented response of Prot-CR or Prot-PR (whichever is earlier) + 1 day]/30.4375. Subjects with a response but no date of death, PD or start of prohibited treatment at the time of analysis

cut-off will be censored at the date of last response assessment. Subjects without a response of Prot-CR or Prot-PR are assigned a duration time of zero.

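### Withdrawing subjects who start other IST leaves follow-up safety, and part of overall proteinuria response, selectively unobserved in the subjects who needed other treatment

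*Protocol*

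**What the plan says.** **Withdrawal.** Protocol 8.8.5 says "Subjects starting on prohibited IST other than MOR202 will be withdrawn from the clinical trial". Subjects withdrawn for this reason in the treatment phase "will immediately be scheduled for their EOT visit (at least 28 days after the last MOR202 dose) and will not enter the follow-up phase". For a subject withdrawn during follow-up, 8.8.5 names no closing visit. Protocol 8.4 is broader, because it covers need as well as start: "MOR202 treatment of subjects in need of immunosuppressive therapies must be discontinued and the subject must be discontinued from the trial". It also bars other IST for the whole duration of the trial.

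**Other ways of stopping.** For toxicity, Protocol 8.8.1 says "Subjects discontinuing MOR202 treatment will have their EOT visit (earliest after 28 days after last dose of MOR202) and enter the follow-up phase". Section 8.8.2 does the same for progressive disease, illness, AEs and a wish to stop MOR202.

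**AE collection after withdrawal.** Protocol 10.8.5 says "Subjects prematurely withdrawn from the clinical trial will be followed up at least until 28 days after last IMP treatment". Under 10.8.10, investigators need not look for events once participation ends, but must report an SAE they learn of and consider related.

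**What is to be estimated.** The third secondary objective is "To assess the safety in subjects with aMN after MOR202 treatment and during the follow-up phase". SAP 11.1 opens the post-treatment AE window on day 29 after the last dose and closes it at study discontinuation. SAP 11.1.3 places all safety tables on the FAS. SAP 7.13.3 defines OPR "irrespective of start of prohibited medication or progressive disease prior to the proteinuria response", whereas best proteinuria response (BPR) stops at prohibited treatment or progression.

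**The concern.** Leaving the trial because other IST is needed is plausibly related to how the subject is doing on MOR202. Cohort 2 is by definition refractory, and no subject is replaced after the safety run-in (Protocol 8.9). For a treatment-phase IST starter, guaranteed AE collection ends just as the post-treatment window opens, yet the subject still counts in the denominator. A reader of the post-treatment AE table would take the percentage as applying to everyone treated.

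The same rule undercuts one SAP definition. An OPR that disregards prohibited medication needs proteinuria values after IST has started. The protocol stops collecting most of them. Protocol 12.6 does not impute missing values and makes multiple imputation optional. The SAP 10.10 sensitivity analysis removes IST recipients, so it cannot recover the missing part either.

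**Working it through.** **1. Post-treatment observation time for a treatment-phase IST starter.** EOT falls 28 to 42 days after the last dose (Protocol 6.5, 10.5). The window opens on day 29. Taking EOT as the end of participation, the subject contributes between 0 days (EOT on day 28) and 42 − 28 = 14 days. A subject with the same EOT who completes follow-up adds 28 × 7 = 196 days. At best the share is 14 / (14 + 196) = 6.7%.

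**2. The plan's own detection figures.** Protocol 12.5 gives 88% (n = 20, incidence 10%) and 80% (n = 10, incidence 15%). Using 1 − (1 − p)^n:
- Cohort 1: 1 − 0.90^20 = 87.8%
- Cohort 2: 1 − 0.85^10 = 80.3%

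Both reproduce. If a share of subjects does not enter follow-up, the probabilities in follow-up are:

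| Not entering | n | Cohort 1 | Cohort 2 |
|---|---|---|---|
| 10% | 18 / 9 | 85.0% | 76.8% |
| 20% | 16 / 8 | 81.5% | 72.8% |
| 30% | 14 / 7 | 77.1% | 67.9% |

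The synopsis expects about 10% premature discontinuation before the end of Week 24, for all reasons. The 20% and 30% rows are assumptions.

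**3. Post-treatment AE incidence.** Assume 60% in IST starters and 30% in others, with no events captured in starters. With d the share starting IST:
- true incidence = 0.60d + 0.30(1 − d)
- FAS table = 0.30(1 − d)
- entrants only = 0.30

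| d | True | FAS | Entrants only |
|---|---|---|---|
| 10% | 33% | 27% | 30% |
| 20% | 36% | 24% | 30% |
| 30% | 39% | 21% | 30% |

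The shortfall on the FAS is 0.60d. Half of it (0.30d) comes from the denominator and disappears if entrants are used. The other half, d × (0.60 − 0.30) = 0.30d, is selection and remains whatever the denominator. The denominator half would arise even if starters had the same AE rate as everyone else.

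**4. OPR.** After baseline, 24-hour UPCR is collected at C4D1, EOT, FUV and EOS (Protocol 10.1). A treatment-phase IST starter can have a value at EOT, and none at FUV or EOS. Take N = 30, about 40% response among those observed, and no response before withdrawal in the rest (assumptions). Counting the withdrawn first as all non-responders, then as all responders:
- 3 withdrawn: 11/30 to 14/30 = 36.7% to 46.7%
- 6 withdrawn: 10/30 to 16/30 = 33.3% to 53.3%
- 9 withdrawn: 8/30 to 17/30 = 26.7% to 56.7%

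The width is the withdrawn fraction itself. A FAS denominator without imputation reports the lower end.

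**The case against.** A reader might infer that follow-up is observed only in subjects who did well. The documents do not support that. Subjects who stop MOR202 for toxicity or progressive disease enter follow-up unless they start other IST. Non-responders who do not start IST stay on schedule. Those who need systemic corticosteroids for more than 7 days may stay on treatment (Protocol 8.4). Subjects who start IST during follow-up contribute data until withdrawal. The missing group is narrower: those removed because they needed or started other IST.

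A reader might also infer that OPR is flattered, or becomes the same as BPR. Neither follows. Counting the withdrawn as non-responders lowers OPR. OPR also disregards progression, and that difference from BPR remains observable because progressors who do not start IST are followed. OPR is not a primary, key secondary or secondary endpoint. SAP 10.3 is redacted, so its denominator cannot be checked.

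The background rates in Protocol section 4 (remission in about 50 to 60% in the first year, relapse in about 25%) describe standard IST. They do not give the share starting IST here.

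Three further points have weight. The 28 days are a minimum, and related SAEs that come to light later must still be reported, so later events are not wholly lost. SAP 9.2 tabulates entry into follow-up and reasons for leaving, so the selection can be seen. AEs under a new immunosuppressant are hard to attribute to MOR202 in an uncontrolled trial of about 30 subjects. These limit the point but do not remove it. Passive reporting does not measure incidence, a disposition table does not supply missing events, and confounding can be displayed only if the data exist.

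**Conclusion.** The point holds in limited form. The withdrawal rule makes the follow-up safety endpoint selectively miss subjects who needed other IST, and the FAS denominator turns their absence into a lower incidence. For treatment-phase IST starters, OPR after EOT is not observed, so OPR as the SAP defines it is probably biased low.

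The size depends on an IST-start rate that the documents do not state. Under the assumed AE rates the FAS figure falls short by 6, 12 or 18 percentage points at 10%, 20% or 30% starting IST, which is 1.8, 3.6 or 5.4 subjects of 30. This is an upper case for those AE rates, because it gives every starter no captured events, whereas follow-up-phase starters contribute some. At 10%, with entrants as denominator, the remaining gap is 33% against 30%, about one subject in 30. The trial tests no hypothesis, so the consequence is a misleading description of late safety rather than a wrong test result. The change is worth making because it is cheap and the lost events cannot be recovered afterwards.

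**What to change.** Leave the MOR202 discontinuation rules unchanged. Reconcile Protocol 8.4 and 8.8.5 so that starting other IST ends study treatment and not observation, as 8.8.1 and 8.8.2 already do for other discontinuers. The scheduled FUV and EOS assessments (AEs, safety laboratory, UPCR, anti-PLA2R) then continue unless consent is withdrawn. The sentence in 8.4 that bars other IST throughout the trial must be reworded to match; otherwise continued observation would contradict it.

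In the SAP:
- Flag all data after IST start.
- Keep best immunological response, BPR and time to response cut at IST start, as now.
- Let OPR use the later data.
- In 11.1.4, show post-treatment AEs before and after IST start, with subjects entering follow-up or person-time as denominator.

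The cost is protocol and SAP wording and at most two already scheduled visits per affected subject. The drawback is that later AEs are confounded by the new IST; the flag and the split make this visible but do not resolve it.

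If visits cannot be added, report the number withdrawn for IST, correct the AE denominator, give bounds for OPR as in step 4, and reconcile SAP 7.13.3 with Protocol 8.4 and 8.8.5.
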